5.5 Clinical and Laboratory Procedures

Prior to starting any procedure associated with this study, the patient or caregiver must give written informed consent ([Appendix C](#)) to participate and agree to abide by the requirements of this study. Study personnel experienced with ASD patients and their families will take great care to explain in detail and in easy to understand terms the purpose, objectives, methods, tests, study schedule, and any other pertinent information that might influence the granting of consent to participate. Similarly, study staff will take great care to elicit and answer all questions that arise in the course of describing this trial and will answer all questions fully. A copy of the consent form will be maintained with the patient's records.

This study will use the local certified clinical laboratory associated with the Investigators practice. CLIA certification and normal values will be obtained by the Investigator and provided to the Sponsor for each clinical lab used, and normal values will be updated after each calibration cycle.

A schedule of events can be found in [Appendix A](#).

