5.5.1.7 Concomitant Medications

As documented in the history and at the screening visit, no patient currently receiving polytherapy for autism will be enrolled in this trial. Any agent which is being prescribed for the treatment of ASD will be noted as such in the eCRF. Subjects identified for accrual into this trial will be weaned to the lowest dose of any prescribed psychotropic medication over the two to four weeks preceding their screening visit deemed effective by the Investigator.

All prescription and nonprescription medication taken by the patient from 14 days prior to screening and up to and including the final visit will be recorded in the medical record and on the eCRF. Any addition, deletion, or change in the dose of these medications must be recorded.

Because the mechanism of L1-79 is the inhibition of catecholamine synthesis, the potential exists for interactions with neurologically active, and other, drugs. Investigators will be diligent in observing potential drug interactions and should appropriately reduce the dose of any concomitant medication that is observed to be potentiated in the presence of L1-79.

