5.5.1.8 Clinical Laboratory Safety Assessments

The following parameters will be measured for the Randomized Groups at screening, at week 4, and at the 4-week follow-up, and in addition for the Assigned Dosage Groups at each weekly visit and the 1 Week Follow up using the central laboratory provided:

- Urinalysis
 - Color
 - Clarity/turbidity
 - pH
 - Specific gravity
 - Glucose
 - Ketones
 - Nitrites
 - Bilirubin
 - Urobilirubin
 - Blood
 - Protein
 - RBC
 - WBC
 - Squamous epithelial cells
 - Casts
 - Crystals
 - Bacteria
 - Yeast
 - Fractionated urinary catecholamines
 - Vanillylmandelic acid
- Hematology
 - hemoglobin,
 - hematocrit,
 - platelet count,
 - RBC
 - WBC with differential
- Serum Chemistry
 - sodium,
 - potassium,
 - chloride,
 - BUN,
 - creatinine,
 - AST,
 - ALT,
 - GGT,
 - LDH,
 - CO₂/bicarbonate
 - total protein,
 - albumin,
 - calcium,

- phosphorous,
- alkaline phosphatase,
- total bilirubin (direct, indirect, total),
- cholesterol,
- triglyceride,
- amylase, lipase
- T₄ & TSH
- Fractionated Plasma Catecholamines
- Metanephhrines, plasma free & fractionated.

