5.9.2.8 Week 8 Follow-Up Visit (Study Day 56)

All patients are to receive:

- Physical exam with vital signs
- Hematology
- Urinalysis
- Serum chemistry
- Blood draw for storage
- ASD assessments will be performed, including: ABC, SRS, RBS-R, CGI-S SAS, VAB II, and CGI-I
- Record all adverse events
- Physical exam with vital signs
 - Question caregiver or patient about the patient's week, including questions regarding any changes in home life activities, events at school, sleep, or other matters germane to an understanding of the patient's autistic
 - Record concomitant medications

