7.3 Dispensing the Study Drug

Study drug will be dispensed as a two week supply during study weeks 0 and 2 visits.. Drugs will be allocated to subjects on a randomized and double-blinded basis. Two containers of 42 doses will consist of the study drug for each patient. Each container will be labeled with the patient's study number.

At the accession visit prior to week 1 and at the post week 2 visit each patient will receive a container of drug corresponding to their study number. Neither the Investigator or the sponsor will know to which dosage group any patient is assigned.

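### Week 4 catecholamine, metanephrine and VMA results reach the site file unmasked while the code is closed, so the Investigator's later ratings and causality judgments could be informed by a treatment marker

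*Combined protocol and SAP*

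**What the plan says.** **What is measured, in whom and when.** Section 5.5.1.8 lists "Fractionated urinary catecholamines" and "Vanillylmandelic acid" under urinalysis. Under serum chemistry it lists "Fractionated Plasma Catecholamines" and metanephrines ("plasma free & fractionated"). The panel applies to the Randomized Groups at screening, Week 4 and the 4-week follow-up. Section 5.9.2.6 and Appendix A confirm safety blood and urine at Week 4 for all patients.

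**Link to treatment.** Section 5.5.1.7 begins its drug-interaction warning: "Because the mechanism of L1-79 is the inhibition of catecholamine synthesis". Section 1.0 says the L-isomer reduces synthesis of dopamine, norepinephrine and epinephrine.

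**Where results go.** Section 5.9.1.3 has copies of all laboratory results kept in each enrolled patient's file. Section 8.2 keeps laboratory reports at the site, sets a 3-day limit for data entry and requires the Investigator to review all database entries. The laboratory itself is described in two ways. Section 5.5 says "This study will use the local certified clinical laboratory associated with the Investigators practice", while 5.5.1.8 refers to a central laboratory.

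**The blind.** Section 7.3 says "Neither the Investigator or the sponsor will know to which dosage group any patient is assigned". Section 5.1.4 keeps the code closed until the last patient in a group has completed the last follow-up visit.

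**Who rates, and when.** The main efficacy endpoint is the Investigator's CGI (3.2.2.1), based on all testing taken together (6.1.5.1). Section 5.9.2.8 schedules at Day 56: "ASD assessments will be performed, including: ABC, SRS, RBS-R, CGI-S SAS, VAB II, and CGI-I". The Investigator also classifies the relation of each adverse event to treatment (5.11).

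**The concern.** These analytes lie directly downstream of the step the drug inhibits. A randomised patient has a screening value and an on-treatment Week 4 value, so the change between them can indicate whether he took active drug. The person who reviews those values is also the CGI rater and the assessor of causality. The plan intends him to be blinded, yet no section withholds these results, routes them to an unblinded third party or provides an independent rater.

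The open-label patients in Groups 1 and 3 have the same panel at every weekly visit. A site that treats them can therefore see the on-drug pattern in known cases.

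If the markers do move with treatment, late CGI ratings and adverse-event attributions in the randomised cohorts could no longer be presented as fully blinded.

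**Working it through.** **1. Is the route to the rater in the documents?** No sentence says that catecholamine results are sent to the Investigator. The route follows from two provisions read together: all laboratory results are in the patient file (5.9.1.3), and reports are held at the site with Investigator review of all entries (8.2). It holds whether the laboratory is local or central, because neither description carries any masking.

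**2. Which assessments come after the Week 4 results?**

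| Item in randomised patients | Timing relative to the Week 4 sample | Exposed? |
|---|---|---|
| CGI at Weeks 1 to 3 | Before | No |
| CGI at Week 4 | Same visit | Normally no |
| CGI-S at Day 56 (5.8, 5.9.2.8, Appendix A) | After | Yes |
| CGI-I at Day 56 (5.9.2.8, Appendix A; 5.8 lists it only at treatment visits) | After, if done | Yes, if done |
| Causality judgments made once results are on file | After | Yes |
| Opinion that the drug is useful enough for rollover (5.1.4) | Not fixed | Possibly |
| SAS (baseline and 4-week follow-up only) | After | Depends on who supplies the score, which is not stated |

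Day 56 is 56 − 28 = 28 days after Week 4. With the ±2-day windows of Appendix A, the shortest gap is 54 − 30 = 24 days. The documents give no laboratory turnaround time, but results would ordinarily be back by then. One of the five post-baseline CGI visits (Weeks 1, 2, 3, 4 and Day 56) is affected.

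**3. How many patients?** There are two cohorts of 15 randomised 2:1, so 2 × 15 = 30 patients: 2 × 10 = 20 active and 2 × 5 = 10 placebo. Within a cohort there are only two arms, so a guess is between active and placebo.

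**4. How much could one marker reveal?** The plan has no figure to reproduce and gives no effect of L1-79 on these analytes. The shift *d*, in SDs of the marker's change from baseline, is therefore an assumption.

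Take the change, signed so that a drug effect is positive, as N(*d*, 1) on active and N(0, 1) on placebo, with prior probability 2/3 for active. The best rule calls a patient active when the change exceeds

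t = d/2 − ln(2)/d,

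and its accuracy is

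(2/3)·Φ(d − t) + (1/3)·Φ(t).

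For d = 1: t = 0.5 − 0.693 = −0.193, and accuracy = (2/3)·Φ(1.193) + (1/3)·Φ(−0.193) = 73.0%.

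The area under the ROC curve is Φ(d/√2).

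| Assumed d | AUC | Best-guess accuracy |
|---|---|---|
| no laboratory data | 0.50 | 66.7% |
| 0.5 | 0.64 | 67.5% |
| 1 | 0.76 | 73.0% |
| 1.5 | 0.86 | 79.6% |
| 2 | 0.92 | 85.5% |

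The gain over always guessing active is about 1, 6, 13 and 19 percentage points. These figures are for one analyte. Several are measured, so they need not be a ceiling.

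**The case against.** **The on-treatment ratings are essentially untouched.** This stands. Weeks 1 to 4 are normally rated before any on-drug catecholamine result exists. What remains is one visit four weeks after dosing ends, plus late causality judgments. Section 5.8 also leaves it unclear whether CGI-I is done at Day 56.

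**The documents are not uniform on these tests.** The synopsis safety list for all groups does not name catecholamines, metanephrines or VMA, and the section on other endpoints presents pharmacodynamic data only for the Assigned Dosage Groups. Section 5.5.1.8 is nevertheless explicit that the Randomized Groups have the panel, and the synopsis list need not be complete.

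**Stronger readings that the documents do not support:**

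- A reader might infer that results come back through the Investigator's own practice laboratory. Section 5.5 suggests this, but 5.5.1.8 says central. The point does not depend on it.
- A reader might treat the anxiety scale as wholly compromised, because its only post-baseline assessment in randomised patients is at Day 56. It is collected after the results are on file, but no section makes the Investigator its rater.
- A reader might use Φ(d/2), which gives 60%, 69% and 84% at d = 0.5, 1 and 2, and compare it with chance at 50%. That midpoint rule suits 1:1 allocation. Under 2:1, always guessing active is already right 66.7% of the time.

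**Safety is primary and the analysis is descriptive.** This also stands and limits the consequence. Adverse-event causality is, however, part of the safety reporting in 6.1.4, so the primary objective is not entirely outside the concern.

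**Conclusion.** The point holds in limited form. Followed as written, the plan places a plausible treatment marker in files that the Investigator must review while he is meant to be blinded, and no section prevents this. The exposure covers the Day 56 CGI ratings, causality judgments made after the Week 4 results arrive and possibly the rollover opinion, in 30 randomised patients.

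How revealing the marker is cannot be settled from the documents. On the single-marker normal model it ranges from almost nothing at 0.5 SD to substantial at 2 SD. The conclusion rests on the stated mechanism, on the inferred reporting route and on results being returned before Day 56. No type I error or power figure is affected, since none is stated. At stake is whether the late comparisons can be described as blinded. This is a cheap improvement worth making.

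**What to change.** - **Section 5.5.1.8:** state that, for randomised patients, post-baseline catecholamine, metanephrine and VMA results are held by the laboratory or data management. They are withheld from site raters and sponsor clinical staff until that cohort's code is broken. State explicitly that they can be released on request in a medical emergency, because 5.1.5 as written provides only the regimen and not laboratory values.
- **Sections 5.9.1.3 and 8.2:** add matching exceptions to the rules on the patient file, on reports held at the site and on Investigator review of entries. Otherwise these sections would contradict the new text.
- **Sections 5.5 and 5.5.1.8:** reconcile the local and central laboratory statements, so that it is clear who carries out the withholding.

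All other safety laboratory results are reported as now, and the withheld values remain available for analysis. The cost is a reporting instruction to the laboratory and short edits in several sections. The downside is small: the site does not see these few analytes during the blinded period.

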5.5.1.9 Blood Draws for Subsequent Testing

- At the time of the sample collection for the analysis of serum chemistry 2 additional red top tubes of blood will be drawn, spun down to separate the cells, and the serum will be frozen and stored for subsequent analysis. Samples will be labeled with the subjects' initials, study number, date of visit, and identified as a pre- or post-treatment sample.
- Frozen serum samples will be stored at the site for up to 7 years and saved for analysis after which they will be destroyed. It is likely that these samples will be analyzed for catecholamine and lipid fractions in the future. However, the precise analysis has yet to be determined, and will be based upon future research results. Separate informed consent will be obtained prior to any future analysis of these specimens, however, all samples will be identified only by protocol and patient numbers. No other patient identifiers will be used.

5.5.1.10 Spense Anxiety Scale

- The Spense Anxiety Scale (SAS) will be administered at baseline and at the 4 week follow-up visit, and also at the 1 wk follow up visit for the assigned dosage groups.

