- **Study Endpoints:** The primary end point will be an assessment of the safety of L1-79 based upon reported adverse events and changes in baseline in physical examination parameters that include orthostatic blood pressure, clinical laboratory measures, and ECGs. Secondary endpoints will include an assessment of pharmacokinetics and pharmacodynamics, as well as the attending physicians assessment as quantified by the Clinical Global Impressions scale based upon

changes from baseline in various psychometric tests, including the Vineland Adaptive Behavior Scale 2nd edition (VABS II, VABS) questionnaire, the Autism Diagnostic Observation Schedule (ADOS), the Aberrant Behavior Checklist-Community (ABC-C), the Spence Anxiety Scale (SAS), the Repetitive Behavior Score – Revised (RBS-R), the Social Responsiveness Scale (SRS), as well as from their personal observations in the clinic, and anecdotally as provided by parents or caregivers over the course of this study.

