3.2.2.2 Additional Efficacy Endpoints

- Changes from baseline in the individual dimensions of the VABS questionnaire
- Changes from baseline in the VABS caregiver rating scale
- Changes from baseline in the ADOS scores and subscores
- Changes in the Clinical Global Impressions scale and subscales.
- Changes in the SAS
- Changes in the SRS
- Changes in the ABC-C scale and subscales
- Clinical opinions of observable changes from baseline.

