5.1.3 RANDOMIZED GROUP

Following the enrollment of 5 open label patients as described in the Assigned Dosage Groups, an additional 15 patients at each dose level will be randomized 2:1 to receive either active drug or placebo (2 active to each placebo patient. These patients will be treated identically to those in the Assigned Dosage Groups with 3 exceptions:

1. No pharmacokinetic samples will be drawn,
2. No EKG will be performed
3. They will not have the 1 week follow-up, just the 1 month follow up.

After being randomized to a treatment arm each patient will be assigned a study number comprised of a 2-digit site identifier and a 3-digit patient identifier as described above.

Study numbers will not be assigned until a patient is qualified and entered into the trial. Screening failures will not be assigned numbers. However, a list of screen failures and their demographic data will be maintained by the Investigator.

Patients will be enrolled and receive their first dose within 3 weeks of completing the screening procedure.

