5.2 Drug Administration

5.2.1 THE L1-79 REGIMEN

Subjects will receive either 100 mg or 200 mg or matching placebo t.i.d. for a total of 28 days of dosing. The doses of L1-79 were determined based upon preliminary clinical research in subjects between 2½ and 24 years of age and doses between 90 and 200 mg t.i.d..

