5.9.2.2 Day 0 Visit

- Subjects will be assigned a randomized study number from a list of study numbers based upon a blinded random assignment of subjects to dosage groups. This study number, consisting of a 2 digit site number and a 3 digit patient number (i.e. XX-YYY) will identify the patient and the drugs allotted to that patient.
- Vital signs
- ASD assessments will be performed, including: ABC, SAS, SRS, RBS-R, CGI-S, & VAB II questionnaire.
- Question caregiver or patient about the patient's week, including questions regarding any changes in home life activities, events at school, sleep, or other matters germane to an understanding of the patient's autistic presentation.
- Assigned Dosage Group patients will also have an EKG, PK and safety blood draws, & 24h urine sample taken prior to dosing, with an additional PK blood draw 1 hour post dosing
- Record concomitant medications
- Record all adverse events
- Dispense 2 weeks of medication

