5.9.2.6 Week 4 Visit (Study Day 28)

- ADOS (all patients) – to be performed during the last week of dosing while patients are still on medication
- Investigators will solicit any adverse events from the patient and/or caregiver and assess
- vital signs
- EKG, Blood and urine samples for PK analysis (Assigned Dosage Group patients only)
- Blood and urine samples for safety analysis for all patients
- Blood drawn for plasma for laboratory studies and for storage
- ASD assessments will be performed, including: ABC, SRS, RBS-R, VABS, CGI-S and CGI-I
- Question caregiver or patient about the patient's week, including questions regarding any changes in home life activities, events at school, sleep, or other matters germane to an understanding of the patient's autistic
- Record concomitant medications
- Record all adverse events

- Confirmation of medication administration and the collection, counting and logging of unused medicine

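### Change in the Spence Anxiety Scale is an efficacy endpoint, but the scale is never given during dosing: the 30 randomised patients have one post-baseline value, nominally 28 days after the last dose

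*Combined protocol and SAP*

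**What the plan says.** Section 3.2.2.2 lists "Changes in the SAS" among the additional efficacy endpoints and names no time point. The synopsis also lists the SAS among the psychometric tests.

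On timing, section 5.5.1.10 says: "The Spense Anxiety Scale (SAS) will be administered at baseline and at the 4 week follow-up visit". It adds the 1-week follow-up for the Assigned Dosage Groups only. The visit lists agree for randomised patients:

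- Day 0 (5.9.2.2) includes it: "ASD assessments will be performed, including: ABC, SAS, SRS, RBS-R, CGI-S, & VAB II questionnaire".
- Weeks 1, 2 and 3 (5.9.2.3 to 5.9.2.5) do not.
- Week 4 (5.9.2.6) does not: "ASD assessments will be performed, including: ABC, SRS, RBS-R, VABS, CGI-S and CGI-I".
- Day 56 (5.9.2.8) does: "ASD assessments will be performed, including: ABC, SRS, RBS-R, CGI-S SAS, VAB II, and CGI-I".

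Row 25 of Appendix A shows the same pattern. Appendix B repeats it for placebo patients who roll over to active drug, with the SAS at rollover baseline and rollover follow-up and none between.

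Two further statements fix the interval. Section 5.2.1 gives the regimen "for a total of 28 days of dosing". Section 5.1.3 says of the randomised patients: "They will not have the 1 week follow-up, just the 1 month follow up".

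**The concern.** The stated purpose (2.1) concerns four weeks of three-times-daily dosing, and the secondary objective (2.2.2) is to compare change from baseline with placebo under blinding. A scale measured before the first dose, and then not until about four weeks after the last, does not observe the treatment period. The documents give no information on how quickly an effect on anxiety would fade. A difference at Day 56 could be a persisting effect or something that arose after withdrawal. The absence of a difference could mean no effect, or an effect that has worn off. A value not collected on treatment cannot be recovered at analysis.

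**Working it through.** **Which visit is meant.** The wording in 5.5.1.10 could be misread as the Week 4 treatment visit. It is not: 5.5.1.8 names Week 4 and the 4-week follow-up as separate occasions, Appendix A gives them separate columns (Day 28 and Day 56), and the SAS mark is in the Day 56 column.

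**Patients.** The synopsis groups sum to the planned total: 5 + 10 + 5 + 10 + 10 = 40. Randomised: 10 + 10 + 10 = 30, which matches 15 at each of two dose levels. Assigned, open label: 5 + 5 = 10.

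**SAS assessments during dosing, after baseline.** Weeks 1, 2, 3 and 4: 0 of 4 visits, in every group.

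**Interval from last dose to the randomised patients' only post-baseline SAS.**

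- Nominal: 56 − 28 = 28 days.
- Assuming dosing lasts exactly 28 days, with the last dose on Day 27 or 28, and applying the ±2-day window at Day 56: 54 − 28 = 26 to 58 − 27 = 31 days.

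**Comparison with the other outcome instruments** (Appendix A, rows 22 and 25 to 32, with the three CGI rows counted as one instrument; the ADI-R is left out because it is used only at screening, for diagnosis):

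| Instrument | Before treatment | Weeks 1–3 | Week 4 | Day 56 |
|---|---|---|---|---|
| ADOS | Screening | No | Yes | No |
| SAS | Day 0 | No | **No** | Yes |
| VABS II | Day 0 | No | Yes | Yes |
| ABC-C | Day 0 | Yes | Yes | Yes |
| SRS | Day 0 | Yes | Yes | Yes |
| RBS-R | Day 0 | Yes | Yes | Yes |
| CGI | Day 0 (severity, overall) | Yes | Yes | Yes |

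Six of seven instruments have a Week 4 value; the SAS is the exception. The VABS II is the closest parallel: it too is omitted at Weeks 1 to 3, but it is repeated at Week 4.

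**Assigned groups.** Appendix A gives these 10 patients an SAS at Day 35, nominally 35 − 28 = 7 days after the last dose. Section 5.9.2.7 also includes it but places the visit at Days 28 to 35. Section 5.1.2 leaves the SAS out of its list of assessments for the same visit. Whether this earlier SAS is taken is therefore not settled by the text. In any case it is after dosing, open label and without placebo.

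**Is a Week 4 visit always on drug?** Not necessarily. The window allows Day 30. If the last dose is on Day 27 or 28, that is 30 − 28 = 2 to 30 − 27 = 3 days after it. Section 5.9.2.6 requires testing on medication for the ADOS only.

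**The case against.** The strongest reply is that nothing here is inconsistent. Sections 5.5.1.10, 5.9.2.2 to 5.9.2.6, 5.9.2.8 and Appendix A agree for randomised patients. The endpoint names no time point, so a Day 0 to Day 56 change satisfies it as written. The study is also safety-primary (2.2.1, 3.2.1), its analysis is descriptive for want of power (6.1), and the SAS is one of eight bullets in 3.2.2.2. All of this stands, and it limits the weight of the point. It does not give the SAS an on-treatment value, and no reason is offered for treating it differently from the other six instruments.

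A reader might go further and infer that the Week 4 CGI, the main efficacy measure, lacks a required input, since the synopsis names the SAS among the tests behind it and 6.1.5.1 refers to all testing in aggregate. The documents do not support that. The synopsis list is open-ended and adds clinic observation and caregiver reports. Neither text requires every test at any one rating. Appendix A also schedules the CGI at Weeks 1 to 3, when the ADOS, VABS II and SAS are all absent, so ratings on a partial set of tests are evidently expected.

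**Conclusion.** The point holds as a mismatch between an endpoint and its schedule. All 30 randomised patients have a single post-baseline SAS in the randomised phase, at Day 56, nominally 28 days after the last dose (26 to 31 days under the assumption stated above). The blinded placebo comparison on anxiety can therefore describe only patients who have stopped treatment. Up to 10 placebo patients who roll over would contribute further SAS values, but again none during dosing.

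The consequence is limited: no safety result and no inferential claim depends on the SAS. No power or test result is claimed here. It would also be too strong to say that the Day 56 value is uninformative. It is a legitimate follow-up measure and can be set beside the other scales given that day. What it cannot do is show an effect on anxiety during treatment, or the lack of one.

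The sections on when the post-baseline ADOS is done (5.7.1.1, 5.9.1.4.2, 5.9.2.6) also disagree. That is a separate item and adds nothing to the weight of this one.

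**What to change.** 1. Add the SAS to the Week 4 visit in 5.5.1.10, 5.9.2.6, Appendix A row 25 and Appendix B. State that it is completed while the patient is still taking study medication, as 5.9.2.6 already does for the ADOS. Without that condition, the visit window could place it after the last dose.
2. In 3.2.2.2, and in the formal statistical plan that 6.1 says is still to be prepared, define SAS change as baseline to Week 4 and report Day 56 as off-drug follow-up.
3. If the SAS is not added, label it a post-treatment follow-up measure, and do not present it as evidence of an on-treatment effect.
4. Reconcile 5.1.2 with 5.5.1.10, 5.9.2.7 and Appendix A on whether the Assigned groups complete the SAS at the 1-week post-dosing visit.

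Cost: one questionnaire at an existing visit, so at most 40 extra forms in the main phase and up to 10 in rollover (40 + 10 = 50 at most), plus a protocol amendment with IRB approval (8.3.3). Relabelling alone adds no forms.
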